8.3.2 Corticosteroid tapering

Participants using concomitant corticosteroids at study entry may begin to reduce their corticosteroid dose to the lowest possible dose/discontinuation beginning at Week 8 until the End of Study as detailed in [Section 6.2.1.1](#) of the protocol.

Successful oral corticosteroid tapering is defined as meeting one of the following:

- Participants with prednisone equivalent dose of > 0.8 mg/kg/day at baseline were able to reduce their dose to ≤ 0.5 mg/kg/day.
- Participants with prednisone equivalent dose from ≥ 0.5 mg/kg/day and ≤ 0.8 mg/kg/day at baseline were able to reduce their dose by at least 0.3 mg/kg/day.
- Participants with any initial prednisone equivalent dose at baseline were able to reduce their dose to ≤ 0.2 mg/kg/day.
- Participants with prednisone equivalent dose of ≤ 0.2 mg/kg/day at baseline were able to reduce their dose with any reduction

AND maintaining a minimum adapted ACR30 response.

8.3.3 Rash assessment

Rash is one of major clinical symptoms of AOSD and typically a salmon-colored rash that occurs along with onset of fever but is transient and disappears at normal body temperature.

The absence or presence of skin rash will be assessed based on physical exam findings including whether it is typical or atypical.

8.3.4 Systemic feature score

Systemic feature score consists of 5 clinical and 5 laboratory assessments. Clinical features include fever, rash, lymphadenopathy, hepatosplenomegaly and serositis. Laboratory features include erythrocyte sedimentation rate, C reactive protein, leucocyte count, hemoglobin level

and platelet count. Each clinical and laboratory feature will be assigned a score of 1 (present) or 0 (absent):

- Fever [defined as a body temperature $>37.5^{\circ}\text{C}$ at least once a day during at least 5 consecutive days]
- Rash [defined by the presence of typical salmon-pink rash on the trunk and elsewhere during the febrile episodes]
- Serositis,
- Lymphadenopathy [defined by lymph node enlargement to >1.5 cm localized anywhere within the body]
- Hepatomegaly and/or splenomegaly that had been confirmed by ultrasound evaluation

Note: Ultrasound sonography for liver and spleen must be performed at baseline, Week 28, Week 48 and EOS visit to assess the presence of hepatomegaly and splenomegaly.

At other assessment visits, palpation will be performed. In case investigator confirmed any findings of hepatomegaly/splenomegaly by palpation, perform ultrasound sonography. If no finding regarding hepatomegaly or splenomegaly is confirmed by palpation, hepatomegaly/splenomegaly is evaluated as “absent”. If there are any findings by palpation but ultrasound sonography is not performed, then hepatomegaly/splenomegaly will be evaluated as “present”.

At baseline, laboratory features were considered present based on the following:

- ESR ≥ 20 mm/hour
- CRP ≥ 10 mg/liter
- White blood cell (WBC) count $\geq 12 \times 10^9$ /liter
- Hemoglobin ≤ 11 g/dl
- Platelet count $\geq 400 \times 10^9$ /liter.

During treatment epochs and at follow up visits, the laboratory parameters were scored as follows:

- ESR, score of 0 if <20 mm/hour or if decreased by $\geq 30\%$ compared to baseline, score of 1 if increased or if decreased by $<30\%$ compared to baseline
- CRP, score of 0 if <10 mg/liter or if decreased by $\geq 30\%$ compared to baseline, score of 1 if increased or if decreased by $<30\%$
- WBC count, score of 0 if $<12 \times 10^9$ /liter or if decreased by $\geq 20\%$ compared to baseline, score of 1 if increased or if decreased by $<20\%$
- Hemoglobin level, score of 0 if >11 g/dl or if increased by $\geq 20\%$ compared to baseline, but score of 1 if decreased or if increased by $<20\%$;
- Platelet count, score of 0 if $<400 \times 10^9$ /liter or if decreased by $\geq 20\%$ compared to baseline, score of 1 if increased or if decreased by $<20\%$.

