
 To evaluate ability of canakinumab to taper corticosteroids based on success criteria starting from Week 8 to Week 28 To evaluate the efficacy of canakinumab with respect to the adapted ACR 30/50/70/90/100 response over time To evaluate the efficacy of canakinumab on the systemic feature score over time To evaluate the efficacy of canakinumab with respect to the components of adapted ACR criteria over time To evaluate ability of canakinumab to taper corticosteroids dose over time after Week 8 To evaluate the efficacy of canakinumab on rash over time To evaluate the efficacy of canakinumab on DAS28-CRP To assess the safety and tolerability of canakinumab 	
 Proportion of participants who are able to taper corticosteroids based on success criteria at Week 28. Proportion of participants who achieved adapted ACR 30/50/70/90/100 response criteria at Day 15 and all subsequent visits. Change from baseline in Systemic Feature Score (total score and each components) at Day 15 and all subsequent visits. Change from baseline in each component of adapted ACR at Day 15 and all subsequent visits Change from baseline of corticosteroid dose at all visits after Week 8. Presence of rash (typical/atypical) at all visits during study. Change from baseline in DAS28-CRP at Day 15 and all subsequent visits. Incidence and severity of Treatment Emergent AEs. Proportion of participants up to end of study with: 
 Adverse events Serious adverse events AEs related to study drug AEs leading to discontinuation Means and mean change over time of: 
 Vital sign parameters Laboratory parameters Canakinumab concentrations over time Total IL-1β (sum of IL-1β free and bound to canakinumab) level s over time Anti-canakinumab antibody identification and titer at BSL, Week 24, Week 48 and every 24 weeks until EOS.

 To evaluate the pharmacokinetics (PK) / pharmacodynamic (PD) of canakinumab To assess the immunogenicity of canakinumab 	

Objective(s)	Endpoint(s)
Exploratory objective(s)	Endpoint(s) for exploratory objective(s)

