Visit Name	Screening	Baseline	Day3	Day 15	Week 4	Week 8	Week12	Week 16	Week 20	Week 24	Week 28	Week 32	Week 36	Week 40	Week 44	Week48	Week 52,56,...	EOS
Days	-28 to -1	1	3	15	29	57	85	113	141	169	197	225	253	281	309	337	Every 4weeks	9999
Electrocardiogram (ECG)	X									X						X	X ¹	X
Physician's global assessment of disease activity (VAS)		X	X	X	X	X	X	X	X	X	X	X	X	X	X	X	X ²	X
Participant's global assessment of disease activity (VAS)		X	X	X	X	X	X	X	X	X	X	X	X	X	X	X	X ²	X
Health Assessment Questionnaire (HAQ)		X	X	X	X	X	X	X	X	X	X	X	X	X	X	X	X ²	X
Tender and swollen joint counts		X	X	X	X	X	X	X	X	X	X	X	X	X	X	X	X ²	X
CRP (local lab)	X	X	X	X	X	X	X	X	X	X	X	X	X	X	X	X	X	X
Fever assessment ³		X	X	X	X	X	X	X	X	X	X	X	X	X	X	X	X	X
Adapted ACR response assessment ³				X	X	X	X	X	X	X	X	X	X	X	X	X	X ²	X
DAS28-CRP		X		X	X	X	X	X	X	X	X	X	X	X	X	X	X ²	X
Systemic feature score ^{3,4}		X		X	X	X	X	X	X	X	X	X	X	X	X	X	X ²	X
Rash assessment		X		X	X	X	X	X	X	X	X	X	X	X	X	X	X	X

CCI

[illegible]

^x Assessment to be recorded in the clinical database or received electronically from a vendor

^s Assessment to be recorded in the source documentation only

¹ Every 24 weeks

² Every 12 weeks

³ Fever will be recorded in the diary and used for Adapted ACR response assessment and Systemic feature score.

⁴ Ultrasound sonography for liver and spleen must be performed at Baseline, Week 28, Week 48 and EOS visit. At other visits, palpation will be performed. In case investigator confirmed any findings of hepatomegaly/splenomegaly by palpation, perform ultrasound sonography.

⁵ Ferritin and fibrinogen will be measured at dosing visits and in case of suspicion of MAS by the investigator.

⁶ Serum pregnancy test is required at Screening. Urine pregnancy tests will be performed at each visit after Baseline visit.

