## **Systemic feature score**

For total score, summary statistics for the observed values and the change/percent change from baseline will be provided by scheduled visit.

For each component score, the number and percentage of participants whose score is 1 (present) will be provided by scheduled visit.

The total score will be calculated by summing the scores of each component and is defined as an integer value 0 to 10. The total score will be calculated only when all components are available.

Each component will be assigned a score of 1 (present) or 0 (absent) as follows:

- Fever [defined as a body temperature  $>37.5^{\circ}\text{C}$  at least once a day during at least 5 consecutive days]
- Rash [defined by the presence of typical salmon-pink rash on the trunk and elsewhere during the febrile episodes]
- Serositis
- Lymphadenopathy [defined by lymph node enlargement to  $>1.5$  cm localized anywhere within the body]
- Hepatomegaly and/or splenomegaly that had been confirmed by ultrasound evaluation

At baseline, laboratory features were considered present based on the following:

- ESR  $\geq 20$  mm/hour
- CRP (observed)  $\geq 10$  mg/liter
- White blood cell (WBC) count  $\geq 12 \times 10^9$ /liter
- Hemoglobin  $\leq 11$  g/dl
- Platelet count  $\geq 400 \times 10^9$ /liter.

During treatment epochs and at follow up visits, the laboratory parameters were scored as follows:

- ESR, score of 0 if  $<20$  mm/hour or if decreased by  $\geq 30\%$  compared to baseline, score of 1 if increased or if decreased by  $<30\%$  compared to baseline
- CRP, score of 0 if  $<10$  mg/liter or if decreased by  $\geq 30\%$  compared to baseline, score of 1 if increased or if decreased by  $<30\%$
- WBC count, score of 0 if  $<12 \times 10^9$ /liter or if decreased by  $\geq 20\%$  compared to baseline, score of 1 if increased or if decreased by  $<20\%$
- Hemoglobin level, score of 0 if  $>11$  g/dl or if increased by  $\geq 20\%$  compared to baseline, but score of 1 if decreased or if increased by  $<20\%$ ;
- Platelet count, score of 0 if  $<400 \times 10^9$ /liter or if decreased by  $\geq 20\%$  compared to baseline, score of 1 if increased or if decreased by  $<20\%$ .

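### Hepato-/splenomegaly in the systemic feature score is sought by ultrasound at baseline but by palpation first at most later visits, so its change from baseline is not like for like; the laboratory items also gain a second route to 0 after baseline

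*Protocol*

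**What the plan says.** Protocol Table 2-1 names as a secondary endpoint: "Change from baseline in Systemic Feature Score (total score and each components) at Day 15 and all subsequent visits". SAP 2.7.2 implements it descriptively: "For total score, summary statistics for the observed values and the change/percent change from baseline will be provided by scheduled visit". It also tabulates, by visit, the number and percentage of participants scoring 1 on each component.

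**Organ item.** Protocol 8.3.4 states: "Ultrasound sonography for liver and spleen must be performed at baseline, Week 28, Week 48 and EOS visit". Footnote 4 of Table 8-1 repeats this. For the remaining visits: "At other assessment visits, palpation will be performed". A palpation finding leads to ultrasound. Two default rules follow:
- A negative palpation scores 0 (absent), under the sentence that begins "If no finding regarding hepatomegaly or splenomegaly is confirmed by palpation, hepatomegaly/splenomegaly is evaluated as".
- A positive palpation with no follow-up scan scores 1 (present).

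SAP 2.7.2 defines the item as ultrasound-confirmed enlargement and does not repeat the palpation rules.

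**Laboratory items.** "At baseline, laboratory features were considered present based on the following": ESR ≥20 mm/hour, CRP ≥10 mg/L, WBC ≥12 × 10⁹/L, haemoglobin ≤11 g/dL, platelets ≥400 × 10⁹/L. After baseline an item scores 0 if it is on the normal side of the same limit, or if it has improved relative to baseline by at least 30% (ESR, CRP) or 20% (WBC, haemoglobin, platelets).

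**Visit mapping.** SAP 2.1.2 and 2.14 map the EOS visit of an early discontinuer to a scheduled visit by time window.

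**The concern.** A change from baseline is interpretable only if both ends are measured the same way. For the organ item they are not at most visits. Ultrasound examines everyone at baseline, while from Day 15 to Week 24 an organ counts only if it is first felt. Any enlargement that palpation misses disappears from the score at Day 15 and returns at Week 28. Steroid tapering may begin at Week 8, so a rise at Week 28 could be taken for disease returning as steroids are withdrawn. The study has one arm, so no comparator would show the same step.

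The laboratory items raise a different question. At baseline 1 means beyond the limit. Later, 0 may mean either back within the limit or improved by 20% or 30% while still beyond it. Subtracting one from the other puts two meanings into a single number.

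**Working it through.** The documents give no expected value or change for this score, so there is no plan figure to reproduce.

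**1. Visits by detection method.** The scored visits from Day 15 to Week 48 in Table 8-1 are Day 15 and Weeks 4, 8, 12, 16, 20, 24, 28, 32, 36, 40, 44 and 48, which makes 13. Ultrasound is mandatory at 2 of them (Weeks 28 and 48), so 13 − 2 = 11 are palpation-first.

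**2. A participant whose enlargement is constant, visible on ultrasound and not palpable.**

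| Visit | Method | Score |
|---|---|---|
| Baseline | Ultrasound | 1 |
| Day 15 to Week 24 | Palpation, negative | 0 |
| Week 28 | Ultrasound | 1 |
| Weeks 32 to 44 | Palpation, negative | 0 |
| Week 48 | Ultrasound | 1 |

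The organ does not change; the item moves by 1 of 10 points each time the method changes.

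**3. Average size.** Let q be the share ultrasound-positive at baseline and s the sensitivity of palpation against ultrasound. With no true change, the mean false fall at a palpation visit is q × (1 − s) points, and the expected number affected is 14 × q × (1 − s). SAP 2.7.2 gives 14 participants for the secondary endpoints. Neither q nor s is in the documents; the ranges below are assumptions.

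| q | s = 0.8 | s = 0.5 | s = 0.3 |
|---|---|---|---|
| 0.2 | 0.04 (0.6 of 14) | 0.10 (1.4) | 0.14 (2.0) |
| 0.4 | 0.08 (1.1) | 0.20 (2.8) | 0.28 (3.9) |
| 0.6 | 0.12 (1.7) | 0.30 (4.2) | 0.42 (5.9) |

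**4. Laboratory items, values unchanged.** Both rules were applied to 200,000 simulated sets of five laboratory values, identical at baseline and follow-up. A value beyond the limit with zero change was read as 1. Baseline and follow-up scores never differed (0 mismatches).

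**5. Laboratory items, partial improvement.** Take ESR 100 to 70, CRP 100 to 70, WBC 20 to 16, haemoglobin 9 to 10.8 and platelets 600 to 480. Every value is still beyond its baseline limit. The protocol rules score 5, then 0. The baseline limits at both times score 5, then 5.

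**6. Laboratory items, random variation only.** For a stable participant well above the limit, with log-normal within-person variation and σ² = ln(1 + CV²):

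P(fall ≥30%) = Φ(ln 0.7 / (√2 σ)) and P(fall ≥20%) = Φ(ln 0.8 / (√2 σ)).

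| CV (assumed) | Fall ≥30% | Fall ≥20% |
|---|---|---|
| 10% | 0.6% | 6% |
| 20% | 10% | 21% |
| 30% | 20% | 30% |
| 40% | 26% | 34% |

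For comparison with fixed limits, a stable group was simulated with assumed median CRP 60 mg/L and between-person log-SD 0.8. At CV 20%, 98.5% score 1 on CRP at baseline. At follow-up 98.5% do so under the fixed limit and 88.7% under the protocol rule. At CV 10% the follow-up figures are 98.6% and 98.1%, so the size depends heavily on the assumed variation.

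**The case against.** The best defence is that the protocol's follow-up rule is a deliberate choice about responsiveness. Fixed limits alone would score a CRP fall from 200 to 12 mg/L as no change. The plan also shows the parts: each component is tabulated by visit, laboratory values and shifts are summarised (SAP 2.8.3), and CRP appears as an adapted ACR component. The score is secondary and untested. All of this stands, and it argues against replacing the laboratory rule in the main analysis. It does not answer the organ item, because a separate table displays the step without removing it.

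A reader might infer more than the documents support:

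- *That the laboratory items fall without any change in the participant.* They do not. The same limits apply at follow-up and unchanged values keep their score. A fall to 0 needs real improvement or random variation.
- *That every difference favours improvement.* A positive palpation without ultrasound is scored present, which is looser than the ultrasound-confirmed definition. The rules also overlap for a value within the limit that has moved the wrong way, with no stated precedence; read literally, this could produce a false worsening.
- *That the CRP ≥10 mg/L entry rule is part of this problem.* A CRP item that starts at 1 and can only improve, and regression to the mean, would remain under fixed-limit scoring.
- *That a false fall and a false relapse will occur.* They occur only if some enlargement is not palpable, and the Week 28 rise also needs that enlargement to persist on treatment.

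**Conclusion.** The concern holds for the organ item. At 11 of the 13 scored visits from Day 15 to Week 48 it is detected differently from baseline, and it can move from 1 to 0 and back with no change in the organ. The effect is bounded at 1 of 10 points per participant and absent at Weeks 28 and 48 and at EOS. Its average, 0.04 to 0.42 points (about 0.6 to 5.9 of 14 participants), rests on assumed values of q from 20% to 60% and palpation sensitivity from 80% to 30%.

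For the laboratory items the supported conclusion is narrower. The change in the total combines features no longer present with features improved but still present, and random variation can add to the fall. That is a matter of interpretation, which a second table can address. The primary test on adapted ACR 30 is unaffected.

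**What to change.** In SAP 2.7.2:

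(a) Report change from baseline in the hepato-/splenomegaly item only at visits with mandatory ultrasound (Week 28, Week 48, EOS). Add a nine-item total that omits this item, with the baseline recomputed on the same nine, at every scored visit, so that one consistent scale runs throughout. Where an EOS visit is remapped to a palpation visit, flag the result by detection method.

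(b) Keep the protocol-defined score as the main analysis. Add a labelled sensitivity table that scores the five laboratory items by the baseline fixed limits at every visit.

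The cost is SAP wording and extra derivations and tables from data already collected, with no new procedure. The improvement shown in the added tables may be smaller than in the main one.

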8.3.5 DAS28-CRP

The DAS28-CRP is a measure of disease activity in Rheumatoid arthritis (RA) based on Swollen and Tender Joints Counts (out of a total of 28), CRP and the Patient's Global

Assessment of Disease ([Prevoo et al 1995](#); [Fransen et al 2003](#)). DAS28-CRP is a composite index, validated for RA patients and takes into account the following items: Tender joint count (number of tender joints; 0-28); swollen joint count (number of swollen joints; 0-28); C-reactive protein (mg/l) and Global Health (Patient's Global Assessment of Disease Activity; from 0=best to 100=worst). Thus, given the reliability, validity, and ability of DAS28 to discriminate the severity of joint involvement, this index has been used in other rheumatic diseases characterized by RA-like poly-articular involvement. Of note, a DAS28 score > 5.1 implies active disease, ≤ 3.2 low disease activity, and < 2.6 remission. Moderate/high disease activity is defined as a DAS28 higher than 3.2.

8.3.6 Appropriateness of efficacy assessments

AOSD is primarily characterized by systemic (including fever) and joint symptoms, and therefore both should be evaluated to assess the therapeutic effect. At this point, however, there are no established measures for systemic symptoms and joint symptoms of AOSD. The adapted ACR Pediatric criteria, which was used in previous Canakinumab clinical trial for SJIA, includes physician/patient's global assessment, patient-reported outcomes, joint assessment, CRP, and presence/absence of fever and enables a comprehensive assessment of systemic symptoms and joint symptoms. The adapted ACR Pediatric criteria are based on the Juvenile Idiopathic Arthritis (JIA) core set developed by the International Leagues of Associations for Rheumatism, and the JIA clinical assessment guideline issued by EMA (EMA 2015) also recommends selecting them as the primary efficacy endpoint.

Among the criteria included in the adapted ACR Pediatric criteria, joints with limitation of motion is characteristic to pediatric assessment. When joint symptoms are assessed in adult patients, including patients with AOSD or RA, in a clinical setting, the presence of tender and/or swollen joints is assessed, whereas limited range of joint motion is not assessed. In consideration of the minor difference in the joint assessment methods between pediatric and adult patients, a total of 6 criteria from the adapted ACR Pediatric criteria, excluding the number of joints with limitation of motion, will be included in the adapted ACR criteria used in this study.

While corticosteroids are the first-line therapy for the treatment of AOSD, reduction of corticosteroid use is desired due to its adverse drug reactions due to long-term use. Therefore, the proportion of patients who achieve reduction of a corticosteroid dose successfully will be assessed as the key secondary endpoint in this study.

8.4 Safety

Safety assessments are specified below with the assessment schedule detailing when each assessment is to be performed.

For details on AE collection and reporting, refer to AE section.

As per [Section 4.6](#), during a Public Health emergency as declared by Local or Regional authorities i.e. pandemic, epidemic or natural disaster, that limits or prevents on-site study visits, regular phone or virtual calls can occur (every 4 weeks or more frequently if needed) for safety monitoring and discussion of the participant's health status until it is safe for the participant to visit the site again.

Assessment	Specification
Physical examination	A complete physical examination will include the examination of general appearance, skin, neck (including thyroid), eyes, ears, nose, throat, lungs, heart, abdomen, back, lymph nodes, extremities, vascular, and neurological. If indicated based on medical history and/or symptoms, rectal, external genitalia, breast, and pelvic exams will be performed. Information for all physical examinations must be included in the source documentation at the study site. Clinically relevant findings that are present prior to signing informed consent must be recorded on the appropriate CRF that captures medical history. Significant findings made after signing informed consent which meet the definition of an AE must be recorded as an AE.
Vital signs	Vital signs will include measurement of participant's body temperature, blood pressure (BP) and pulse. Body temperature (axillary, oral, or rectal) will be measured by the Investigator at each visit. In addition, participant will measure body temperature axillary, orally or rectally during occurrence of fever and record it in the participant's diary from the occurrence until one day after resolution. Systolic and diastolic BP and radial pulse rate will be assessed after the participant has rested in the supine position for at least 3 minutes. BP should be assessed on the same arm each time measurements are taken. These data will be recorded in the eCRF. At the baseline visit, a triplicate blood pressure measuring technique will be implemented. Systolic and diastolic blood pressure will be measured three times. The repeat sitting measurements will be made at 1-2 min intervals and the mean of the three measurements will be used. Clinically notable vital signs are defined in Appendix 1.
Height and weight	Height in centimeters (cm) and body weight (to the nearest 0.1 kilogram (kg) in indoor clothing, but without shoes) will be measured as indicated in Table 8-1 . If possible, body weight assessments should be performed by the same study site staff member and using the same scale throughout the study.

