##### **Baseline**

Baseline is the last assessment (including screening visits and unscheduled visits) obtained before the first administration of the study treatment.

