#### **2.8.4.2 Vital signs**

Vital signs will be summarized by presenting descriptive statistics for the absolute values and changes from baseline by scheduled visit. Change from baseline will be summarized for participants with both baseline and post baseline values.

Incidence rates of notable abnormalities newly occurred after baseline (see [Section 5.4](#)) at any visit (including the unscheduled visits) will be presented. A listing for participants satisfying at least one criterion for notable abnormalities newly after baseline will be listed by participant and visit.

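### Baseline blood pressure averages in sitting repeats while later readings follow a supine rule, and the SAP does not say which baseline value is used

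*Protocol*

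**What the plan says.** The vital-signs entry in Protocol 8.4 gives a general rule that is not tied to any visit: "Systolic and diastolic BP and radial pulse rate will be assessed after the participant has rested in the supine position for at least 3 minutes". It then adds a procedure for one visit only: "At the baseline visit, a triplicate blood pressure measuring technique will be implemented". The next sentences read "Systolic and diastolic blood pressure will be measured three times" and "The repeat sitting measurements will be made at 1-2 min intervals and the mean of the three measurements will be used". The one consistency rule concerns the arm, not the posture: "BP should be assessed on the same arm each time measurements are taken".

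Protocol Table 2-1 makes vital signs part of a secondary safety endpoint, described as "Means and mean change over time of" vital-sign and laboratory parameters. SAP 2.8.4.2 implements it: "Vital signs will be summarized by presenting descriptive statistics for the absolute values and changes from baseline by scheduled visit". SAP 5.4 and Protocol Appendix 1 also flag systolic or diastolic BP that rises or falls by 25% or more from baseline.

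SAP 2.1.1 has one definition of baseline for all assessments: "Baseline is the last assessment (including screening visits and unscheduled visits) obtained before the first administration of the study treatment". It mentions neither the triplicate nor posture.

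**The concern.** The same entry in the protocol gives two postures for the same measurement, and the second applies only at the visit from which all change is counted. If sites follow the text, the way BP is measured changes at first dose. Any systematic difference between sitting and supine BP then enters every post-baseline change in one direction. It also moves the point at which the 25% flags are triggered. The trial has a single arm, so no comparator carries the same offset and would let a reader see it.

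A second gap lies in the SAP. The protocol says the mean of three is used; the SAP says the last assessment is used. Read literally, the SAP could pick the third reading, which is one of the repeats described as sitting. This needs settling even if posture was uniform.

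What is at stake is the reading of descriptive BP tables that support a registration dossier. No hypothesis test depends on them.

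**Working it through.** The plan gives no figure of its own to reproduce. What can be derived is the share of the posture difference that reaches the tables.

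**Inputs from the documents:** three baseline readings with the mean used, repeats sitting, general rule supine (Protocol 8.4); 25% flag (SAP 5.4); no control arm (Protocol 3).

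**Assumed:** d, the sitting-minus-supine difference, from -10 to +10 mmHg; true supine BP S of 120 mmHg systolic and 75 mmHg diastolic. None of these is in the documents.

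**Offset in change from baseline, no drug effect.** The later reading is S.

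- First reading supine by the general rule, two repeats sitting: baseline = (S + 2(S + d))/3 = S + (2/3)d, so change = -(2/3)d.
- All three readings sitting: baseline = S + d, so change = -d.
- SAP rule read literally, third reading sitting: baseline = S + d, so change = -d.

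| Assumed d (mmHg) | Mixed mean: spurious change | All sitting, or last reading only: spurious change |
|---|---|---|
| -10 | +6.7 | +10 |
| -5 | +3.3 | +5 |
| -2 | +1.3 | +2 |
| 0 | 0 | 0 |
| +2 | -1.3 | -2 |
| +5 | -3.3 | -5 |
| +10 | -6.7 | -10 |

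**Effect on the 25% flags, mixed mean.** With baseline B = S + (2/3)d, the upper flag needs a true rise of 1.25B/S - 1, and the lower flag a true fall of 1 - 0.75B/S.

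- Systolic, S = 120, d = -10: B = 113.33. Rise needed 1.25 × 113.33/120 - 1 = 18.1%; fall needed 1 - 0.75 × 113.33/120 = 29.2%.
- Systolic, d = +10: B = 126.67. Rise needed 31.9%; fall needed 20.8%.
- Diastolic, S = 75, d from -10 to +10: rise needed 13.9% to 36.1%; fall needed 31.7% to 18.3%.

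With d = 0 every one of these is 25%.

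**Why a single matched reading is a poor baseline for the flags.** Suppose readings are independent with common variance v, and later visits have one reading. Change from a single baseline reading has variance v + v = 2v. Change from a mean of three has variance v + v/3 = (4/3)v. The ratio of standard deviations is √(2 ÷ 4/3) = √1.5 = 1.22. Readings minutes apart are likely to be correlated, which brings the ratio closer to 1. A single supine reading removes the offset but widens the spread, so it can raise the rate of false 25% flags.

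**The case against.** The strongest reply is that the word sitting may be left over from other text. If sites applied the supine rule to every reading there is no offset, and the defect is one word. That cannot be excluded, because the documents do not show what sites did. It limits the conclusion to what the written instruction would produce, but the instruction still contradicts itself and nothing else in either document resolves it. Protocol 12.5.3 mentions flagging relevant orthostatic changes, but that does not explain the wording: 8.4 averages the three readings and does not compare postures.

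It is also fair to say that the later visits are nowhere described as single readings. That follows only from the triplicate being confined to baseline. The posture of the first baseline reading is not stated either.

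A reader might infer more than the text supports:

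- **That all vital signs are affected.** Only BP is in the triplicate. Pulse follows the supine rule throughout, and temperature does not depend on this procedure.
- **That the bias equals the whole posture difference.** If the first reading is supine and the mean is used, it is two thirds.
- **That the trial would report posture as a drug effect.** The outputs are descriptive, no BP test is planned, and the sign and size of the difference are unknown.
- **That correcting 8.4 repairs the data.** Protocol 3 records the decision to stop enrolment, and the SAP counts 14 participants in all (2.5.6). Rewording cannot change baseline readings already taken.

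**Conclusion.** The point holds as an internal contradiction in Protocol 8.4, together with an unstated derivation in the SAP. As written, BP change from baseline and the 25% flags may contain two thirds of the sitting-minus-supine difference, or all of it if every baseline reading was sitting or only the last one is taken. Those multipliers come from the text. The millimetre values rest on an assumed difference, since the documents give none, and on sites having followed the wording. The primary endpoint, its test and the other efficacy endpoints do not use BP. The matter is modest in weight but worth correcting, because the tables have no control arm and the correction is cheap.

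**What to change.** 1. **Protocol 8.4.** Reconcile the sentences so that one posture applies to all BP readings, including the baseline triplicate. Which posture is for the sponsor to state. This is a one-line correction for any further amendment.
2. **SAP 2.1.1 or 2.8.4.2.** State that baseline BP is the mean of the baseline-visit readings taken in the same posture as the post-baseline readings, where posture and individual readings were recorded.
3. **Where they were not recorded.** Keep the mean of three and footnote the BP change and notable-abnormality tables, saying that baseline may include sitting readings.
4. **Where only one reading matches.** It may be shown as a sensitivity summary for mean change. Keep the mean of three for the 25% flags, for the reason given in the working.

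The cost is a check of what was captured at baseline, one SAP derivation line and a footnote. No new data are needed.
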